### **8.6.3. Clinical Laboratory Evaluations**

Clinical laboratory evaluations will be performed as detailed in the SoEs in Section 1.3.

The clinical laboratory tests will include hematology, coagulation, blood chemistry, and urinalysis. Refer to Section 10.2 for the complete list of laboratory parameters.

Abnormal laboratory values occurring during the clinical study will be followed until repeat test results return to normal (or baseline), stabilize, or are no longer clinically relevant. New or worsened clinically relevant laboratory abnormalities should be recorded as AEs.

### **8.6.4. Physical Examinations**

Height, weight, and calculation of BMI and physical examinations will be performed as detailed in the SoEs in Section 1.3.

A full physical examination should include an evaluation of the head, eyes, ears, nose, and throat and the cardiovascular, dermatological, musculoskeletal, respiratory, gastrointestinal, and neurological systems.

Any abnormality in physical examination identified at baseline and any abnormalities that are changes from baseline should be recorded. New or worsened clinically relevant abnormalities should be recorded as AEs.

### **8.6.5. Vital Signs**

Vital signs will be performed as detailed in the SoEs in Section 1.3.

Allowable time windows for vital sign assessments are provided in Section 10.7.

Vital signs will include the measurements of respiratory rate, heart rate, systolic and diastolic blood pressures, and temperature. Vital signs will be measured after the subject has rested in a supine position for at least 5 minutes, prior to laboratory draws, and at the same timepoints as ECGs.

### **8.6.6. Electrocardiograms**

Electrocardiograms will be performed as detailed in the SoEs in Section 1.3.

Allowable time windows for ECGs are provided in Section 10.7.

Tripple 12-lead ECGs (approximately 2 minutes apart) will be performed at least 5 minutes before any blood collection and will be recorded for every subject. The ECG will be measured after the subject has rested in a supine position for at least 5 minutes. At any visit during which a subject exhibits a heart rate  $\leq 50$  bpm or other clinical indications for ECG, the ECG will be repeated. Abnormal, clinically relevant findings occurring post-baseline will be reported as AEs. Whether or not the measurement is performed, the date the ECG is performed, heart rate, PR interval, RR interval, QRS amplitude, QT interval, QTcF interval, and results will be recorded.

## **8.7. Pharmacogenomic (Inherited Genetic) Analysis**

A single blood sample for pharmacogenomic analysis will be collected predose from each randomized subject for Treatment Group A and for Treatment Group B. Detailed instructions for the collection, handling, and shipping of samples are outlined in the Laboratory Specifications Document as detailed in Section 10.6.

Genetic analyses will not be performed on blood samples collected for PK or safety assessments. Subject confidentiality will be maintained.

DNA samples will be stored, as outlined in Section 8.7.2, for performing possible pharmacogenomic analysis in the future, otherwise all remaining DNA samples will be destroyed.

### **8.7.1. Banking of Specimens for Inherited Genetic Analysis**

Procedures for the longterm preservation (banking) of blood and/or DNA specimens extracted from subjects' blood samples for each subject that consented are described in the Section 10.6.

The banked samples may be analyzed for genes involved in absorption, distribution, metabolism, elimination, safety, and efficacy of quizartinib. Additionally, samples may be analyzed for genes involved in quizartinib related signaling pathways, or to examine diseases or physiologic processes related to quizartinib. DNA samples will not be immortalized or sold to anyone. This information may be useful in increasing the knowledge of differences among individuals in the way they respond to the study drug, as well as helping in the development of new drugs or improvement of existing drugs.

### **8.7.2. Storage and Disposal of Specimens**

Banked DNA samples will be stored for a maximum of 15 years after the finalization of the clinical study report for this protocol. These specimens will be kept for pharmacogenetic analysis in case new genomic or genetic information is obtained in the future regarding the response (PK or pharmacodynamic) to quizartinib, or in case serious adverse drug reactions are noted in a clinical study and pharmacogenetic analysis is to be conducted for investigation into the cause.

During the storage period, the samples will be coded with labels having no personal information and will not be immortalized or sold to anyone. Subjects will have the right to withdraw consent and have their sample destroyed at any time. However, the data will not be discarded if analysis has been completed before the subject withdraws consent.

### **8.7.3. Disclosure of the Results of Future Pharmacogenetic Analysis**

Because the nature and value of future pharmacogenetic analysis cannot be known at this time, any results obtained from research involving pharmacogenetic samples will not be disclosed to the subject or Investigators now or in the future.

## **9. STATISTICAL CONSIDERATIONS**

### **9.1. Statistical Hypothesis**

This is not a hypothesis testing study.

### **9.2. Sample Size Determination**

The number of subjects planned for this study was not based on statistical power considerations.

With the assumed intersubject coefficient of variation (CV) of 35%, a target sample size of 30 (15/treatment) was calculated to provide 90% confidence that the estimated ratios (with and without efavirenz) of quizartinib geometric mean Cmax and AUC values would be within 20% of true population values. Therefore, 32 subjects (16 subjects in Treatment Group A and 16 subjects in Treatment Group B) will be enrolled in the study to target at least 30 subjects to complete the PK evaluation.

### **9.3. Exposure and Compliance**

As the dose administration is under the control of the study sites, compliance to study medication will not be an issue. Study drug administration will be summarized by subject, treatment, and time of dosing.

## **9.4. Population for Analysis Sets**

### **9.4.1. Pharmacokinetic Population**

The PK analysis will be conducted on the PK Population defined as all evaluable subjects who are dosed and who have sufficient data to calculate at least 1 of the planned PK parameters.

### **9.4.2. Safety Population**

The safety analysis will be conducted on the Safety Population defined as all subjects who receive at least 1 dose of study drug.

## **9.5. Statistical Analysis**

The statistical analysis plan (SAP) will be developed and finalized before database lock and will describe the subject populations to be included in the analyses, and procedures for accounting for missing, unused, and spurious data. This section is a summary of the planned statistical analyses of the primary and secondary endpoints.

### **9.5.1. Efficacy Analysis**

No efficacy measures or analysis are planned for this study.

### **9.5.2. Safety Analysis**

#### **9.5.2.1. Adverse Events**

Treatment-emergent adverse events (TEAEs) are defined as new AEs that occur after the first dose of study drug. AEs collected 30 days after the last dose of study drug will not be considered

TEAEs unless they are treatment-related. AEs will be coded using the MedDRA dictionary. An AE will be assigned to the study day in which it started, even if it resolved on a subsequent day. The incidence of TEAEs will be summarized by treatment group. The number and percentage of subjects reporting TEAEs will be calculated overall, by system organ class, by preferred term, and by treatment group.

Treatment-emergent adverse events will be further summarized by CTCAE grade and relationship to study drug or AEs that were present prior to the first dose but which worsened in severity after the first dose of study drug. Similarly, the number and percentage of subjects reporting treatment-emergent SAEs and related treatment-emergent SAEs will be tabulated, treatment-emergent AESIs, and TEAEs leading to discontinuation of study drug.

A by-subject AE (including treatment-emergent) data listing including but not limited to verbatim term, preferred term, system organ class, CTCAE grade, and relationship to study drug will be provided. Deaths, SAEs, AESIs, and AEs associated with study drug discontinuation will be listed.

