## 8.6.2. Adverse Events

### 8.6.2.1. Method to Detect Adverse Events

The definitions of an AE or SAE can be found in Section 10.4. Adverse events may be directly observed, reported spontaneously by the subject or by questioning the subject (or, when appropriate, by a caregiver, surrogate, or the subject's legally authorized representative) at each study visit. Subjects should be questioned in a general way, without asking about the occurrence of any specific symptoms. The Investigator must assess all AEs to determine seriousness, severity, and causality. The Investigator and any qualified designees are responsible for

detecting, documenting, and recording events that meet the definition of an AE or SAE and remain responsible for following AEs that are serious, considered related to the study drug or study procedures, or that caused the subject to discontinue.

All clinical laboratory results, vital signs, and ECG results or findings should be appraised by the Investigator to determine their clinical significance. Isolated abnormal laboratory results, vital sign findings, or ECG findings (i.e., not part of a reported diagnosis) should be reported as AEs if they are symptomatic, lead to study drug discontinuation, lead to dose reduction, require corrective treatment, or constitute an AE in the Investigator's clinical judgment.

Medical conditions (including laboratory values/vital signs that are out of range) that were diagnosed or known to exist prior to informed consent will be recorded as part of medical history.

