#### **8.6.2.2. Time Period for Collecting Adverse Events, including AESIs and Serious Adverse Events**

For all randomized subjects, all AEs occurring after the subject signs the ICF and that are followed to resolution up to 30 days after the EOS, whether observed by the Investigator or reported by the subject, will be recorded as detailed in Section 10.1.6.2. All SAEs will be followed until resolution, stabilization, the event is otherwise explained, or the subject is lost to follow-up.

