#### **10.4.1.1. Events Meeting the AE Definition**

- Any abnormal laboratory test results (hematology, clinical chemistry, or urinalysis) or other safety assessments (e.g., ECG, radiological scans, vital signs measurements), including those that worsen from baseline, considered clinically relevant in the medical and scientific judgment of the Investigator (i.e., not related to progression of underlying disease).
- Exacerbation of a chronic or intermittent pre-existing condition including either an increase in frequency and/or intensity of the condition.
- New conditions detected or diagnosed after study intervention administration even though it may have been present before the start of the study.
- Signs, symptoms, or the clinical sequelae of a suspected drug-drug interaction.
- Signs, symptoms, or the clinical sequelae of a suspected overdose of either study intervention or a concomitant medication.

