#### 10.4.3. Grade Assessment

The severity of AEs will be graded using the latest NCI-CTCAE (version 5.0). For each episode, the highest severity grade attained should be reported.

The NCI-CTCAE guidelines do not allow certain grades for certain AEs. For example, pain can be Grade 1 to 3 only (i.e., cannot be life-threatening or fatal), whereas sepsis can only be Grade 4

or 5 (i.e., can only be life-threatening or fatal). In addition, alopecia can only be Grade 1 or 2. The NCI-CTCAE guidelines should be followed closely.

- Grade 1: Mild AE
- Grade 2: Moderate AE
- Grade 3: Severe AE
- Grade 4: Life-threatening consequences; urgent intervention indicated
- Grade 5: Death related to AE

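### The TEAE definition covers only new events, while the next paragraph of Section 9.5.2.1 also counts pre-dose events that worsened, so the TEAE tables rest on different event sets

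*Combined protocol and SAP*

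**What the plan says.** All of this is in the protocol; Section 9.5 defers detail to a separate SAP.

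- **Definition (Section 9.5.2.1, first paragraph).** TEAEs "are defined as new AEs that occur after the first dose of study drug". Worsening is not mentioned.
- **Incidence tables (same paragraph).** "The number and percentage of subjects reporting TEAEs will be calculated overall, by system organ class, by preferred term, and by treatment group".
- **Start-day rule (same paragraph).** "An AE will be assigned to the study day in which it started, even if it resolved on a subsequent day".
- **Grade and relationship summaries (Section 9.5.2.1, second paragraph).** The sentence describing these adds "AEs that were present prior to the first dose but which worsened in severity after the first dose of study drug". The clause is attached by a stray *or* and does not parse.
- **Collection window (Section 8.6.2.2).** The protocol collects "all AEs occurring after the subject signs the ICF", so AEs with onset before dosing can be in the database.
- **Grading (Section 10.4.3).** "For each episode, the highest severity grade attained should be reported".
- **Worsening of existing conditions (Section 10.4.1.1).** The events that qualify as AEs include "Exacerbation of a chronic or intermittent pre-existing condition including either an increase in frequency and/or intensity of the condition".

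**The concern.** TEAEs are the first-listed secondary endpoint (Section 3.2). If the definition is limited to new events but a later summary admits worsened pre-dose events, two programmers can derive two different TEAE flags from the same page. The grade and relationship tables could then contain a subject who is absent from the tables by system organ class and preferred term. The missing class is not arbitrary: worsening after dosing of something already present is one of the things a treatment-emergent definition is meant to catch.

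The recording rules do not settle the matter. Section 10.4.3 asks for one grade per episode, and Section 9.5.2.1 ties an event to its start day. Neither says whether a worsening opens a new record or what date it carries. Whether the event is counted may therefore depend on how the site happens to enter it.

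**Working it through.** The plan states no figure on this point, so there is nothing to reproduce. The check applies two rules to each kind of AE.

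**Inputs.** First dose of study drug: Day 1 in both groups, because Table 6.1 lists efavirenz as well as quizartinib as a study drug and Group A starts efavirenz on Day 1. Collection starts at consent (Section 8.6.2.2). Group size: 16 planned, with 15 per group as the target for completing the PK evaluation (Section 9.2).

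**Rules.** *Literal*: a TEAE is a record with onset after the first dose. *Inclusive*: a TEAE is an AE that starts or worsens after the first dose.

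| Kind of AE | Literal | Inclusive |
|---|---|---|
| Starts after first dose, does not worsen | TEAE | TEAE |
| Starts after first dose, worsens later | TEAE | TEAE |
| Group A: starts in efavirenz lead-in (Days 1 to 14), worsens after Day 15 | TEAE | TEAE |
| Starts between consent and first dose, worsens after dosing, kept as one record | **not a TEAE** | **TEAE** |
| Starts before first dose, worsening entered as a new AE | TEAE | TEAE |
| Medical-history condition, exacerbation entered as an AE after dosing | TEAE | TEAE |
| Starts before first dose, does not worsen | not a TEAE | not a TEAE |

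The rules differ in one row of seven. In that row the second paragraph of Section 9.5.2.1 counts the event and the first paragraph does not.

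**Size per affected subject.** Incidence is subjects with an event divided by n. If the subject has no other TEAE in that table row, the change is 1/n:

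- n = 16: 1/16 = 6.25 percentage points.
- n = 15: 1/15 = 6.67 percentage points.

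If the subject already has a TEAE in that row, the change is zero.

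**Number affected.** The documents give no rate of AEs between consent and first dose. As an assumption, take 0 to 2 such subjects, all in one group and none with another TEAE in the row. The shift is then between 0 and 2 × 6.25 = 12.5 percentage points.

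**Group A attribution.** A lead-in event that worsens after quizartinib is in the tables, but as one episode with a start day in the lead-in and its highest grade. Section 10.4.5 splits Group A causality into efavirenz alone and the combination. The start day and peak grade alone do not show on which side of the Day 15 dose the worsening fell.

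**The case against.** The strongest reply is that this is a misplaced clause. The words about worsened pre-dose AEs read naturally as the second half of the definition, so the intent is visible. Section 9.5 calls itself a summary, and a SAP is to be finalized before database lock. That stands as far as intent goes, and it is why the repair is small. It does not remove the conflict in the current text. The later SAP text is not available to judge. A SAP can also harmonize a definition but cannot supply dates of worsening that were never captured.

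A second reply is that worsening may be entered as a new AE anyway. Section 10.4.1.1 makes exacerbation of a pre-existing condition an AE, and Sections 8.6.3 and 8.6.4 require worsened, clinically relevant laboratory and examination findings to be recorded as AEs. Conditions "that were diagnosed or known to exist prior to informed consent will be recorded as part of medical history", so their later exacerbation would be a new AE. This stands, and it narrows the gap. But none of these sections says that an AE already open is closed and re-entered when it worsens. Conversely, a rule of one record per event is not written down either; it is an inference from the highest-grade sentence in Section 10.4.3.

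A reader might infer something stronger: that every event which worsens after dosing drops out of the incidence tables, or that Group A lead-in events are lost once quizartinib is given. The documents do not support either. An event that starts after the first dose is a TEAE whether or not it worsens, and in Group A the first dose is efavirenz on Day 1. The start-day rule removes nothing by itself; it only fixes the onset of an episode that is not re-recorded. Nor can the number of Group A subjects with an event ongoing at Day 15 serve as a measure of loss. The documents give no such rate, and ongoing events are neither necessarily worsened nor missing.

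Safety review also does not rest on these tables alone. The plan has by-subject AE listings, CTCAE shift tables for laboratory tests (Section 9.5.2.2), and ECG summaries by scheduled time with QTc categories (Section 9.5.2.3).

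**Conclusion.** The point holds in a narrow form. Section 9.5.2.1 is internally inconsistent about which events are TEAEs. Followed literally, its incidence tables omit AEs that begin between consent and first dose, worsen after dosing, and stay as a single episode. The effect is 6.25 percentage points of group incidence per affected subject at n = 16, provided that subject has no other TEAE in the row. The number affected is unknown and probably small, since the subjects are healthy and the window is the 21-day Screening Period up to dosing on Day 1.

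The conclusion rests on two assumptions: that the definition sentence is programmed as written, and that the site does not open a new record at worsening. Group A lead-in events remain in the tables. What is incomplete for them is only the timing of any worsening relative to the Day 15 dose. That is a reason for a modest improvement in data capture, not evidence of lost events.

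**What to change.** 1. Move the worsening clause into the definition: a TEAE is an AE that starts, or worsens in CTCAE grade, after the first dose of study drug.
2. Delete the stray clause from the second paragraph of Section 9.5.2.1, and use the one definition for every TEAE table. Carry the same wording into the SAP.
3. As a cheap improvement, instruct sites to record the date of any grade increase, and reconcile that instruction with the highest-grade rule in Section 10.4.3. In Group A this would identify lead-in events that worsened after the Day 15 quizartinib dose, in line with the causality categories in Section 10.4.5. The instruction should be in place before enrolment, because the dates cannot be relied on if sought afterwards.

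Items 1 and 2 cost one sentence and no extra data. Item 3 costs an eCRF completion instruction and a few more AE records.

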- c A full physical examination that includes an evaluation of the head, eyes, ears, nose, and throat and the cardiovascular, dermatological, musculoskeletal, respiratory, gastrointestinal, and neurological systems will be performed at Screening, and on Day -1, Day 14, and EOS.
- d BMI at Screening only
- e Female subjects (WOCBP only)
- f Naturally postmenopausal female subjects only
- g Blood samples for hematology and serum chemistry will be collected after a 10-hour fast at Screening, and on Day -1, Day 7, predose (quizartinib) on Day 15, and on Day 19, Day 27, and EOS.
- h Triuplicate ECG (approximately 2 minutes apart) and after at least 5 minutes of quiet rest in the supine position. When a blood collection is scheduled concomitantly with an ECG, the ECG should be taken at least 5 minutes prior to the blood collection and at predose, 2, 4, and 8 hours after quizartinib administration.
- i Vital signs will be taken after at least a 5-minute supine rest; vital signs should be taken at all ECG timepoints.
- j Efavirenz will be dosed as 600 mg once daily from Day 1 through Day 35. Efavirenz will be taken before bedtime on an empty stomach (no food for at least 2 hours before and after dosing).
- k A single dose of 60-mg quizartinib (2 × 30 mg) will be administered following an overnight fast of 10 h on Day 15. Water consumption will be restricted from 1 hour predose to 2 hours postdose, except for the 240 mL of water that is to be administered with quizartinib. Subjects will continue to fast for 4 hours postdose.
- l Day 15 through 36 (relative to quizartinib) PK samples for quizartinib will be collected at predose, 1, 2, 4, 6, 8, 12, 24, 48, 72, 96, 144, 216, 288, 360, 432, and 504 hours post-quizartinib dose. Quizartinib and AC886 showed temperature- and concentration-dependent partitioning into blood cells; therefore, blood samples must be processed at room temperature for determination of plasma quizartinib and AC886 concentrations.

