#### 4.1.1. Design Overview

In this study, 32 eligible subjects will be randomized in a 1:1 ratio to 1 of 2 treatment groups; 16 subjects in Treatment Group A and 16 subjects in Treatment Group B.

At the beginning of the Screening Period, subjects will sign the informed consent form (ICF). During the 21-day Screening Period, subjects' eligibility will be confirmed. They will undergo medical history evaluation, physical examination, vital sign determination, ECGs, and clinical laboratory assessments.

During the Treatment Period, subjects will receive study drug in the assigned treatment group.

Treatment Group A: On Day 1, subjects will begin a regimen of 600-mg efavirenz tablet once daily and will continue the regimen through Day 35. Efavirenz will be taken before bedtime on an empty stomach (no food for at least 2 hours before and after dosing). On Day 15, subjects will receive a single dose of 60-mg quizartinib ( $2 \times 30$  mg), which will be administered with 240 mL of water after at least 10 hours of fasting. Quizartinib will be taken in the morning. Subjects will continue to fast for 4 hours postdose. Pharmacokinetic blood samples will be collected from Day 15 through Day 36. Subjects will be discharged from the CRU and from the study at end-of-study (EOS) on Day 36 after study procedures are completed. Safety assessments will be conducted from Day 1 through Day 36.

Treatment Group B: On Day 1, subjects will be given a single dose of 60-mg quizartinib ( $2 \times 30$  mg) with 240 mL of water after 10 hours of fasting. Quizartinib will be taken in the morning followed by an additional 4 hours of fasting. Pharmacokinetic blood samples will be collected from Day 1 through Day 22. Subjects will be discharged from the CRU and from the study at EOS on Day 22 after study procedures are completed. Safety assessments will be conducted from Day 1 through Day 22.

After study treatment is discontinued, subjects will be followed for 30 days for safety.

The subject population is described in Section 5. A flow diagram of study activities is presented in Figure 1.1.

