#### **4.1.2. End-of-Study**

At the defined EOS in both treatment groups (Day 36 for Treatment Group A and Day 22 for Treatment Group B), subjects will have a final PK blood sample taken and safety assessments of AEs, laboratory tests, vital signs, ECGs, and physical examination conducted.

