## 6. STUDY TREATMENT(S)

### 6.1. Study Drug(s) Description

Table 6.1: Study Drug Dosing Information

Study Drug Name	Quizartinib	Efavirenz
Dosage Formulation	30-mg tablet a	600-mg tablet
Dosage Level(s)	60 mg	600 mg
Route of Administration	Oral	Oral
Dosing	Single dose	Once daily
Duration	Once	Once daily for 35 doses
Packaging	High-density polyethylene (HDPE) bottles of 30 tablets  Packaging will clearly display the name of product, storage condition, and other required information as applicable in accordance with local regulations	Bottles of 30 tablets
Labeling	Bottles will be labeled as required per local and regulatory requirements	Bottles will be labeled as required per local and regulatory requirements

a Each 30-mg tablet contains 30-mg quizartinib dihydrochloride (26.5 mg free base).

Quizartinib will be supplied by the Sponsor, and efavirenz will be supplied by Worldwide Clinical Trials (Worldwide).

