### **6.3.2. Blinding**

This is an open-label study.

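### Sections 4.1.1, 8.6.2.2 and 9.5.2.1 end the adverse event period at different points, and the TEAE rule covers 50 post-quizartinib days in Group A but 30 in Group B

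*Combined protocol and SAP*

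**What the plan says.** Three places in the protocol bear on when the adverse event (AE) period ends.

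- Section 9.5.2.1 starts treatment-emergent status at the first dose of study drug and closes it as follows: "AEs collected 30 days after the last dose of study drug will not be considered" "TEAEs unless they are treatment-related". TEAE incidence is then tabulated by treatment group, and the treatment-emergent SAE and AESI counts use the same status.
- Section 8.6.2.2, whose heading concerns the time period for collecting AEs, covers "all AEs occurring after the subject signs the ICF and that are followed to resolution up to 30 days after the EOS".
- Section 4.1.1 says that safety follow-up lasts 30 days once study treatment has been discontinued.

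The dates that drive these rules differ by group. EOS is "Day 36 for Treatment Group A and Day 22 for Treatment Group B" (Section 4.1.2). In Group A, "Efavirenz will be dosed as 600 mg once daily from Day 1 through Day 35" (Table 1.1, footnote j), and Section 4.1.1 adds "On Day 15, subjects will receive a single dose of 60-mg quizartinib". In Group B the only dose is quizartinib on Day 1. Efavirenz is a study drug: it has its own column in "Table 6.1: Study Drug Dosing Information". On blinding, Section 6.3.2 states "This is an open-label study".

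**The concern.** EOS falls 21 days after quizartinib in both groups, so a window tied to EOS is symmetric around quizartinib. A window tied to the last dose of any study drug is not, because Group A continues efavirenz for 20 days after quizartinib and Group B has no further dose.

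The secondary objective is the safety of quizartinib alone and with efavirenz, and readers will set the two columns of the TEAE table side by side. An unrelated AE 40 days after quizartinib falls on Day 55 in Group A and is a TEAE. In Group B it falls on Day 41 and is not. After the cut-off an AE enters the table only if it is judged treatment-related by an investigator who knows the assignment. The causality categories also differ by group: Section 10.4.5 uses efavirenz alone or the combination in A, and quizartinib alone in B. Part of any difference between the columns could therefore reflect the counting rule.

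**Working it through.** **Check on the day numbering.** Section 4.1.4 gives durations of up to 58 and 44 days. Screening days + check-in + EOS day gives 21 + 1 + 36 = 58 and 21 + 1 + 22 = 44. Both reproduce, and both stop at EOS, with no 30-day follow-up included.

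**Inputs.** Quizartinib day: A 15, B 1. Last dose of study drug: A 35 (efavirenz), B 1 (quizartinib). EOS: A 36, B 22.

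**TEAE window under Section 9.5.2.1.** Cut-off = last dose + 30.

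- Group A: 35 + 30 = Day 65, and 65 − 15 = 50 days after quizartinib.
- Group B: 1 + 30 = Day 31, and 31 − 1 = 30 days after quizartinib.

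**Effect under each reading of collection.** Filtered days are collected days later than the cut-off, on which an AE counts only if called related.

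| Collection runs to | Last day, A / B | Post-quizartinib days collected, A / B | Filtered on causality, A / B | Counted for any cause, A / B |
|---|---|---|---|---|
| EOS + 30 (8.6.2.2 read as collection) | 66 / 52 | 51 / 51 | 1 / 21 | 50 / 30 |
| End of treatment + 30 (4.1.1) | 65 / 31 | 50 / 30 | 0 / 0 | 50 / 30 |
| EOS only (8.6.2.2 read as follow-up of known AEs) | 36 / 22 | 21 / 21 | 0 / 0 | 21 / 21 |

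In the first row the filtered share is 1/51 = 2.0% in A (Day 66) and 21/51 = 41.2% in B (Days 32 to 52).

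**Sensitivity to wording.** If the 30th day is itself excluded, the filtered days become 2 and 22 of 51, and the gap of 20 days is unchanged. If last dose meant quizartinib only, the Group A cut-off would be 15 + 30 = Day 45, with 21 of 51 days filtered in A as well, and the asymmetry would vanish. Table 6.1 does not support that reading.

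**Illustration of size.** The documents give no background AE rate. Assume a constant daily hazard h of a first AE, and full reporting after discharge. Incidence = 1 − exp(−h × days).

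- h = 0.2%: 9.5% over 50 days, 5.8% over 30 days, a gap of about 4 points.
- h = 0.5%: 22.1% and 13.9%, a gap of about 8 points.
- h = 1%: 39.3% and 25.9%, a gap of about 13 points.

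Expected Group B events on filtered days = 16 × h × 21 = 0.7, 1.7 and 3.4. These are upper-end figures, since late reporting will be thinner than assumed.

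**The case against.** The strongest objection is that little may be collected in the disputed days. The wording of 8.6.2.2 can be read as a limit on following AEs already recorded. Subjects are discharged from the study at EOS, the stated durations end there, and Tables 1.1 and 1.2 show no visit or contact afterwards. If new AEs stop at EOS, the imbalance is zero. This stands as a real possibility, but the heading of 8.6.2.2 and the 30-day follow-up in 4.1.1 point the other way, and the text does not settle it.

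Second, 4.1.1 matches the 9.5.2.1 cut-off exactly, so the analysis rule may discard nothing. That is right, but the post-quizartinib coverage is still 50 days against 30. Aligning collection with 9.5.2.1 would remove the contradiction between sections and leave the comparison unequal.

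Third, a window tied to the end of the assigned regimen is coherent. Day 55 in Group A is only 20 days after efavirenz. Day 31 in Group B is 720 h after quizartinib, about 9.9 effective half-lives of the parent (73 h) and 6.1 of AC886 (119 h). This supports keeping a table by regimen. It does not make that table a like-for-like comparison after quizartinib.

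Fourth, the study tests no hypothesis (Section 9.1), safety is descriptive, related late AEs still count, and the by-subject listing holds all AEs. All of this stands and limits the consequence to the summary tables.

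A reader might infer that 21 of 51 Group B days are certainly filtered, or that Group A incidence is inflated by 4 to 13 points. The documents support neither. The first holds only if 8.6.2.2 governs collection of new AEs, and the second rests on assumed constant hazards through a period with no scheduled contact.

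**Conclusion.** The three sections give inconsistent end points and need to be reconciled. As written, the 9.5.2.1 rule closes the all-cause TEAE window 50 days after quizartinib in Group A and 30 days after it in Group B, so the by-group incidence tables can count unequal post-quizartinib time. AEs collected beyond the cut-off enter only on an open-label causality judgement, and nearly all such days would be in Group B.

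This assumes that efavirenz counts as a study drug, as Table 6.1 indicates, and that new AEs are taken after EOS. On the second assumption the documents are unclear. The effect is likely small: 16 subjects per group, no scheduled contact after EOS, and complete listings. It is a definable imbalance that can be removed before the SAP is final, not a demonstrated bias in the safety results.

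**What to change.** 1. Reconcile Sections 4.1.1, 8.6.2.2 and 9.5.2.1 so that one statement says until when new AEs are collected, kept distinct from how long known AEs are followed.
2. Keep the TEAE start at the first dose of study drug, and tabulate Group A's efavirenz-only AEs (before the Day 15 quizartinib dose) as their own period. Starting every TEAE table at quizartinib would drop those events.
3. Add a between-group summary that counts all AEs, regardless of causality, from the quizartinib dose to the same number of days after it in both groups. Use 51 days if collection to EOS + 30 is confirmed. Otherwise use the longest window collected in both groups: 30 days under 4.1.1, or 21 if new AEs stop at EOS.
4. List later AEs separately, whatever their causality.

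The cost is a few sentences in Section 9.5.2.1 and the SAP, which Section 9.5 says is still to be finalized before database lock, plus one extra table. A few late unrelated AEs will be added or moved. The summary uses whatever window is collected, so it requires no additional visits or data.
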